5.2 Definitions

- Disease-free survival (DFS) will be defined as the time length from the date of surgery to the date of tumor recurrence or death (tumor recurrence as reported on follow-up pages in the eCRF, death as reported in the end of study page in the eCRF). Patients that had no tumor recurrence and did not die will be censored at the date of last contact when patient was alive (as reported on the end of study page in the eCRF).
- Overall survival (OS) will be calculated as the time length from the date of surgery to the date of death. Patients that did not die will be censored at the date of last contact when patient was alive (as reported on the end of study page in the eCRF).
- For both DFS and OS the following rule will be applied for incomplete dates: The date of surgery is assumed to always be completely known (day, month and year available), otherwise DFS and OS will not be calculated. For the end dates (death, tumor recurrence, last date patient was alive) patients will be secured at the earliest possible date. E.g. if the date of death is "UK/05/2019" then the patient is censored at 01/05/2019 and thus being considered event-free until this date and status is considered unknown after

this date. If this rule results in negative survival time, the patient is not considered for Kaplan-Meier analysis.

• Δ tumor size will be defined as the difference [mm] between "current SUM LD" and "baseline sum LD" on the tumor response assessment page of the eCRF.

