8.1 Trial design and hypotheses

The study is designed as an open-label, single arm, prospective, monocentric, phase II study of pembrolizumab in a neoadjuvant setting in patients with non-small cell lung cancer of Stage II/IIIA suitable for curative intent surgery. It is formally hypothesized that pembrolizumab applied in the neoadjuvant setting is feasible and safe and additionally a clinically meaningful pilot data for efficacy can be observed. On a preliminary basis, feasibility will be declared if the rate of successfully performed resections without extended delays is ≥80% (Feasibility criterion).

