2.8 Handling Missing Data

In general, missing data will not be imputed and analysis is restricted on available data, with the following exceptions:

- For time-to-event endpoints (DFS, OS), incomplete dates will be handled as described in Section 5.2.
- Response rates will consider missing response assessments as described in Section 5.2.
- Missing causality assessment for adverse events will lead to handling of the AE as related (see Section 7.3 . of the CSP)

2.9 **Protocol Deviations**

Potential protocol deviations will be collected prior to database snapshot for the main analysis. Potential protocol deviations will be discussed in a data review meeting (DRM) prior to database snapshot for the main analysis and will be classified as relevant or not relevant. A protocol deviation will be considered relevant if it has a potential influence on the efficacy analysis. Relevant protocol deviations will lead to exclusion from the PP Population. Relevant protocol deviations can be one of the following but are not limited to:

- at least one of the major inclusion criteria was not met (criteria with relevant impact on efficacy)
- at least one of the major exclusion criteria was fulfilled (criteria with relevant impact on efficacy) •
- administration of prohibited therapies during the screening and treatment phase as defined in the CSP •
- administration of no study treatment •
- no documentation of tumor assessment after start of study treatment •
- erroneous dose of study medication .

Medical Coding 2.10

All information regarding the medical coding of medical history and adverse events can be found in the coding guideline.

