5. EFFICACY ANALYSIS

Efficacy analyses will be performed primarily on the PP Population and will be repeated on the the ITT population.

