| 16.2.4.16 | Surgeries performed (Safety Population) | Patient ID, Surgery performed, Date of surgery, |
| | | Method, Approach, Extensions, Systematic lymph |
| | | node dissection performed, Intraoperative blood |
| | | loss [m]], Intraoperative blood transfusion |

| | | performed, Post-operative complications, Length |
|-----------|---|---|
| | | of ICU stay, Re-admission to ICU, Date of re- |
| | | admisson |
| 16.2.4.17 | Vital signs (Safety Population) | Patient ID, Visit, Parameter, Value, Unit |
| 16.2.4.18 | Cardiac evaluation (Safety Population) | Patient ID, Visit, Evaluation performed, Cardiac |
| | | evaluation, Date, Result, Specification of |
| | | abnormality |
| 16.2.4.19 | ECOG performance status (Safety Population) | Patient ID, Visit, Date ECOG Score, ECOG Score |
| 16.2.4.20 | Routine Chest X-Ray (Safety Population) | Patient ID, Visit, Chest X-Ray performed, Date of |
| | | performance, Tumor visible, Comments |
| 16.2.4.21 | Pregnancy test (Safety Population) | Patient ID, Visit, Pregnancy test performed, Date |
| | | of test, Reason not performed, Method, Result |
| 16.2.4.22 | Quality of Life (Safety Population) | Patient ID, Visit, Date of assessment, Quality of |
| | | Life question, Answer/Result |

Page 23 of 23

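### SAP 5.2 treats operated patients left with tumor as disease-free until recurrence is reported or they die, so DFS can be overstated

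*SAP*

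**What the plan says.** SAP 5.2 holds the only definition of DFS. Protocol 2.5 names the endpoint, and Protocol 8.4.3 leaves the details of secondary parameters to the SAP. The definition reads "Disease-free survival (DFS) will be defined as the time length from the date of surgery to the date of tumor recurrence or death". Recurrence means "tumor recurrence as reported on follow-up pages in the eCRF", and death is taken from the end-of-study page. For everyone else: "Patients that had no tumor recurrence and did not die will be censored at the date of last contact when patient was alive". The one stated condition for entering the analysis is a complete surgery date; "otherwise DFS and OS will not be calculated".

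On the analysis set, SAP 5 says "Efficacy analyses will be performed primarily on the PP Population", with a repeat in the ITT population. Neither Protocol 8.3.2 nor SAP 2.9 and 2.11.2 names an aborted or incomplete resection as a reason for exclusion from PP. The list in SAP 2.9 is open, however: "Relevant protocol deviations can be one of the following but are not limited to".

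The surgery listing (16.2.4.16 in SAP 7.2.4) begins "Patient ID, Surgery performed, Date of surgery" and continues with method, approach, extensions, node dissection, blood loss and transfusion, complications and intensive care stay. Neither it nor the histology listing (16.2.3.5) has a field for margins or residual tumor.

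SAP 5.3 plans Kaplan-Meier medians and rates at time points such as 12, 24 and 36 months with 95% limits, and no tests.

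**The concern.** DFS presupposes that surgery left the patient free of disease, and the SAP definition never checks this. Tumor left in place is persistence, which the definition does not list as an event. Under the rule as written, such a patient therefore contributes disease-free time until recurrence is reported or the patient dies.

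The schedule does not ensure that this happens early. The end-of-treatment visit is 6 weeks after surgery (Protocol 3.2) and the first follow-up visit is 3 months later (Protocol 5.2.6), roughly four and a half months after surgery. The follow-up column of the schedule of assessments marks survival status, subsequent cancer therapy and continuing adverse events, and no imaging.

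Protocol 1.4 names loss of resectability through delay as the general risk of a neoadjuvant strategy. A failed resection is the last outcome that should earn disease-free credit. DFS is one of only two secondary endpoints, and its time-point rates will be read as a description of how patients did after resection.

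**Working it through.** **1. The plan's own figure.** The documents give no DFS figure. The only precision statement behind N = 30 (Protocol 8.2, SAP 1.4) is that an event with incidence above 9.5% is seen at least once with 95% probability. Check: 1 − (1 − 0.095)^30 = 0.9499. It reproduces, but it does not bear on the DFS rule.

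**2. Could such patients occur?** The documents give no rate of aborted or macroscopically incomplete resection. Taking 5% or 10% as assumptions, the chance of at least one among 30 is 1 − 0.95^30 = 78.5% or 1 − 0.90^30 = 95.8%.

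**3. SAP rule against an event-at-surgery rule.** Let n be the number operated, k those with no resection or macroscopic residual tumor, s the share of the k with no recorded event at time t, and R the DFS of the other n − k at time t. Assume no censoring before t.

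- SAP rule: [(n − k) × R + k × s] / n
- Event at surgery: (n − k) × R / n
- Difference: (k/n) × s

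R drops out. The difference is never negative, and it is zero if k = 0 or s = 0. Per affected patient the ceiling (s = 1) is 1/30 = 3.3 points or 1/27 = 3.7 points. Thirty is the target sample size; 27 operated is an assumption.

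**4. SAP rule against completely resected patients only.** Treat the other n − k as the completely resected. The difference is then (k/n) × (s − R), so its sign depends on R. For illustration, take the 52% five-year relapse rate in Protocol 1.3 and assume an exponential curve: R at 24 months = 0.48^(24/60) = 74.6%. With n = 30 and s from 0 to 1:

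| k | SAP rule, 24 months | Event at surgery | SAP minus event at surgery | SAP minus completely resected only |
|---|---|---|---|---|
| 1 | 72.1 to 75.4% | 72.1% | 0 to +3.3 | −2.5 to +0.8 |
| 3 | 67.1 to 77.1% | 67.1% | 0 to +10.0 | −7.5 to +2.5 |
| 6 | 59.6 to 79.6% | 59.6% | 0 to +20.0 | −14.9 to +5.1 |

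The row k = 6 takes the 20% unresectability threshold of Protocol 5.4 as an outer limit (0.20 × 30 = 6). That threshold also counts patients never operated on or operated on too late, so 6 is not an expected number. In the last column the SAP figure is too high only if s exceeds 74.6%.

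**The case against.** The strongest reply is that nothing shows any bias will occur. It needs at least one such patient, and that patient must not be entered promptly as recurrent. Protocol 3.3 says follow-up collects information on relapse, and Listing 16.2.3.11 has a recurrence field with a date of diagnosis. An entry dated close to surgery would make s almost zero. For a thoracotomy without resection, the effect also depends on whether the eCRF records it as surgery with a date, which the documents do not say. The open list in SAP 2.9 would let the data review meeting remove such patients from PP. The endpoint is secondary and descriptive, with no threshold attached.

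All of this stands, and it limits the claim to what can happen. It does not supply the missing rule. A PP exclusion decided at the meeting would be unspecified in advance and would leave the ITT repeat unchanged.

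Three stronger readings are tempting, and the documents do not support them.

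- *DFS is overestimated.* This is conditional, as above, and the upward direction holds only against an event-at-surgery rule.
- *The affected patients cannot be identified.* Listing 16.2.3.5 records whether regression grading was done and, if not, why; Listing 16.2.4.16 records the surgical method. Non-resection may be inferable from these. What is missing is a direct record of completeness, above all after an actual resection.
- *DFS contradicts the feasibility criterion.* Protocol 8.1 says "feasibility will be declared if the rate of successfully performed resections without extended delays" is at least 80%. It does not mention margins or residual tumor, and a proportion and a time-to-event endpoint need not agree.

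The link to loss of resectability also has a limit. Tumor is reassessed before surgery (Protocol 3.1), and patients never operated on have no surgery date. They get no DFS at all, so they are not held event-free. Their absence from the ITT repeat is a separate matter.

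**Conclusion.** The rule in SAP 5.2 is faulty for a small, definable group: operated patients with no resection or with macroscopic residual tumor. As written, it credits them with disease-free time that they never had. Against an event-at-surgery rule the excess is (k/n) × s: nil if there are no such patients, otherwise 0 to 3.3 points each with 30 operated, or 0 to 3.7 with 27. The upper ends require every affected patient to be alive with no recurrence recorded at the time point. Against a completely-resected-only analysis the sign is open.

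These sizes rest on assumed values of n, k and s and on no early censoring. The 24-month illustration also assumes an exponential curve. What stands without any of these is that the estimate lacks a stated treatment of patients who were never disease-free. That is worth correcting, in proportion to a descriptive secondary endpoint.

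**What to change.** - In SAP 5.2, count an operated patient with no resection or with macroscopic residual tumor, as shown by the operation and pathology reports, as a DFS event on the date of surgery.
- Report the number of such patients beside the DFS results.
- Repeat the Kaplan-Meier analysis in completely resected patients as a supportive analysis. Since the direction of any difference depends on the comparator, the reader needs both. State where microscopic residual tumor falls: under this wording it is not an event at surgery, but it would not qualify as complete resection.
- Add completeness of resection to Listing 16.2.4.16.

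The cost is SAP wording, one field taken from existing reports and one added analysis. DFS may look slightly less favourable. No visit, treatment or sample size changes.

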5.2.6 Follow-up

AIO-Studien-gGmbH

After discontinuation of treatment, all patients will be followed-up for survival every 3 months. First visit of the follow-up period will take place 3 months after EOT visit. Follow-up of the individual patient will continue until death or until study is terminated. The following information will be collected during the follow-up:

- Survival data
- Subsequent anti-cancer therapy
- Study drug related adverse events continuing from treatment phase will be followed-up until the event has resolved or stabilized

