5.3 Inferential Analysis

No statistical tests are performed due to the small sample size.

DFS and OS will be described by means of Kaplan-Meier method. Estimates of median DFS and OS rates for specific time points (at e.g. 12, 24 and 36 months) will be provided with the associated 95% confidence limits.

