Page 21 of 23

| 16.2.3.10 | Translational research (ITT Population) | Patient ID, Visit, Blood sample for biomarkers |
|-----------|---|--|
| | | drawn, Date of blood sample drawn |
| 16.2.3.11 | Survival status/ Follow-up (ITT Population) | Patient ID, Visit, Patient alive, Tumor |
| | | recurrence, Date of diagnosis, CT thorax scan |
| | | performed, X-ray performed |

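### SAP 5.2 censors DFS at the last date known alive rather than the last date recurrence status was known, so DFS is overestimated whenever survival contact outlasts recurrence assessment

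*SAP*

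**What the plan says.** SAP 5.2 measures DFS from surgery to recurrence or death. Its two event types come from different pages: "tumor recurrence as reported on follow-up pages in the eCRF, death as reported in the end of study page in the eCRF". For patients with neither event the rule is: "Patients that had no tumor recurrence and did not die will be censored at the date of last contact when patient was alive". The date is read from the end-of-study page. The OS rule uses the same date: "Patients that did not die will be censored at the date of last contact when patient was alive".

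SAP 5.3 adds that "DFS and OS will be described by means of Kaplan-Meier method", with rates "for specific time points (at e.g. 12, 24 and 36 months", and that "No statistical tests are performed due to the small sample size". Protocol 8.4.3 specifies only Kaplan-Meier curves and leaves the details to the SAP.

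The documents describe follow-up in several ways:

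- Protocol 3.3: 3-monthly evaluations collect relapse, survival status and later cancer treatment.
- Protocol 5.3: patients who withdraw consent for treatment only are still followed for progression and survival.
- Protocol 5.2.6: "all patients will be followed-up for survival every 3 months". Its list of data to collect has survival, later anticancer therapy and continuing drug-related adverse events, but not recurrence.
- Schedule of assessments (protocol, repeated in SAP 1.5): the follow-up column has adverse-event follow-up, later therapy and survival status. It has no tumor assessment.
- SAP 7.2.3, Listing 16.2.3.11: by visit, whether the patient is alive, then tumor "recurrence, Date of diagnosis, CT thorax scan" and X-ray performed.

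**The concern.** A DFS time is known to be event-free only up to the last point at which recurrence was assessed. Knowing that a patient is alive is enough for OS but not for DFS. The SAP applies the OS censoring date to DFS, and nothing ties that date to the last known recurrence status. Any interval between the two is credited as disease-free.

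The SAP is more cautious elsewhere in the same section. With an incomplete end date, it censors at the earliest possible date and treats later status as unknown. The DFS censoring rule does not apply that reasoning to recurrence status.

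At stake are the DFS rates at the planned time points. In a single-arm study without tests, the rate itself is what readers will set against historical figures, such as the 52% 5-year relapse rate in Protocol 1.3. Where there is an error, it always favors the treatment.

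**Working it through.** The documents give no DFS rate, event count or power, so there is no DFS figure to reproduce. The check covers direction first, then size.

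**Direction.** The Kaplan-Meier estimate is S(t) = Π(1 − d_j/n_j) over event times up to t. Compare the SAP rule with censoring at the last recurrence assessment, counting the same recurrences and deaths under both. The d_j are then identical. The SAP rule censors at the same time or later, so each n_j is equal or larger, each factor is equal or larger, and S(t) can never be lower. In 3,000 simulated trials of 30 patients there were no exceptions. If no patient has a gap, the two curves are identical.

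**Inputs from the documents**

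- Relapse of 52% at 5 years (Protocol 1.3).
- At least 24 months of follow-up for the last patient (Protocol 3.4) and about 36 months of accrual (Protocol 3.7), so follow-up runs from 24 to 24 + 36 = 60 months.
- N = 30 (Protocol 3.5).

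**Assumptions not in the documents**

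- Exponential time to recurrence and uniform follow-up.
- The length of the gap and the share of patients affected.
- No deaths, except where stated.

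**Reference curve.** The hazard is −ln(1 − 0.52)/60 = 0.0122 per month. DFS is exp(−0.01223 × 24) = 74.6% at 24 months and exp(−0.01223 × 36) = 64.4% at 36 months.

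**Size.** Large-sample Kaplan-Meier estimates, each accurate to about 0.2 points:

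| Scenario | SAP rule, 24 / 36 months | Last-assessment rule, 24 / 36 months |
|---|---|---|
| No gap | 74.5 / 64.4% | 74.5 / 64.4% |
| 3-month gap, all patients | 74.6 / 65.3% | 74.5 / 64.2% |
| 6-month gap, all patients | 75.1 / 66.8% | 74.6 / 64.3% |
| 12-month gap, all patients | 76.5 / 70.3% | 74.6 / 64.4% |
| 10% stop checks at 3-18 months | 75.9 / 66.7% | about 74.6 / 64.4% |
| 20% stop checks at 3-18 months | 77.3 / 69.2% | about 74.6 / 64.4% |
| 30% stop checks at 3-18 months | 78.7 / 71.5% | about 74.6 / 64.4% |

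For the 3-month gap the excess is 74.6 − 74.5 = 0.1 point and 65.3 − 64.2 = 1.1 points. For the early-stopping rows it runs from 75.9 − 74.6 = 1.3 to 78.7 − 74.6 = 4.1 points at 24 months, and from 66.7 − 64.4 = 2.3 to 71.5 − 64.4 = 7.1 points at 36 months.

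The timing of stopping matters. If checks instead stop at a random time during follow-up in 20% of patients, the SAP rule gives 76.1 / 67.2% against 74.7 / 64.4%, an excess of 1.4 / 2.8 points.

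**Scale.** The 95% half-width for 74.5% with N = 30 is 1.96 × √(0.745 × 0.255/30) = 15.6 points.

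**Is the alternative neutral?** Not fully once deaths are added. Take a 12-month gap in all patients and a median of 12 months from recurrence to death. At 36 months the fully observed curve is 64.4%. The SAP rule gives 68.8%. The last-assessment rule, with deaths in the gap still counted as events, gives 62.3%, which is 2.1 points too low.

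**The case against.** The strongest reply is that the plan intends no gap. Protocol 3.3 makes relapse part of each 3-monthly evaluation, Protocol 5.3 keeps following progression after treatment is stopped, and Listing 16.2.3.11 places vital status and recurrence on the same visit record. No survival-only follow-up status is defined. If visits run this way, the bias is about 0 to 1 point. The 10-30% shares and the 3-18 month window come from no passage.

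Most of this stands. A reader might infer that DFS will certainly be overestimated, or that recurrence is not collected in follow-up. The documents support neither: the bias is zero when last contact is also a recurrence check, and the listing shows that recurrence is recorded by visit. What remains is that Protocol 5.2.6 and the schedule's follow-up column permit a contact that confirms only survival, and the SAP rule has no safeguard when that happens.

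A second reply is that little depends on DFS. It is a descriptive secondary endpoint, no test is planned, and the feasibility and early-stopping criteria (Protocol 8.1 and 5.4) concern resection. That also stands. A reader might infer that a trial decision could be swayed, but no decision rule uses DFS. Sampling error is also several times the bias in the plausible scenarios. It falls in either direction, however, whereas this bias can only go upward.

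**Conclusion.** The point holds conditionally. SAP 5.2 overestimates DFS whenever vital-status contact outlasts recurrence assessment and leaves it unaffected otherwise. The direction follows from the estimator and needs no assumptions. The size does need them: 52% relapse at 5 years, exponential times, 24-60 months of follow-up and an assumed gap. On that basis the excess is about 0.1 point at 24 months and 1.1 points at 36 months for a 3-month gap in everyone. It is about 1-4 and 2-7 points if 10-30% of patients stop recurrence checks 3-18 months after surgery. Against a half-width of about 16 points this is modest. It is worth correcting because it can only flatter the treatment, and because the data for a better rule are already collected.

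**What to change.** In SAP 5.2:

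1. Censor DFS in living, recurrence-free patients at the last follow-up visit with documented recurrence status, or at the surgery date if there is none. Listing 16.2.3.11 holds the data.
2. Keep last-alive censoring for OS.
3. State how a death after missed recurrence assessments is handled. Counting every such death as an event while survivors are censored back can push DFS slightly downward.
4. Report the present rule as a sensitivity analysis.

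In the protocol, reconcile 3.3, 5.2.6 and the schedule's follow-up column on whether recurrence is collected at each follow-up visit.

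The cost is a few SAP sentences, one extra DFS analysis and an alignment of the protocol text. No new data are needed if the follow-up pages are completed as the listing implies. The downside is slightly shorter DFS follow-up in some patients. The rule relies on recorded recurrence status, so it does not by itself make the checks more thorough.

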3.4 End of Study

All enrolled patients will be followed up until the end of the study. The study will be terminated as soon as the last patient has completed at least 24 months of follow-up.

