2. GENERAL CONSIDERATIONS

2.1 Conduct of Analysis

Two analyses will be performed for this study.

- Main analysis will be performed after all patients had their end of treatment, data entry for all visits except the follow-up visits is complete, data were cleaned, a Data Review Meeting was performed and database snapshot has been completed.
- Addendum analysis will be performed after last patient completed the entire study, follow-up data entry and cleaning are complete and database was closed.

Main analysis will summarize all data recorded up to the time of the database snapshot. Addendum analysis will only present data captured during follow-up. This means, the addendum analysis may only include overall survival, end of study details and subsequent cancer therapy. An SAE listing will also be prepared to show possible follow-up information of SAEs ongoing after end of treatment.

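### The DFS and OS censoring date is taken only from the end-of-study page, which event-free patients probably lack at the main analysis; the addendum, when they would have it, does not list DFS

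*SAP*

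**What the plan says.** **Censoring and event sources (SAP 5.2).** For DFS: "Patients that had no tumor recurrence and did not die will be censored at the date of last contact when patient was alive". For both endpoints the date is the one on the end-of-study page: patients without the event are "censored at the date of last contact when patient was alive (as reported on the end of study page in the eCRF"). Events have two sources: "tumor recurrence as reported on follow-up pages in the eCRF, death as reported in the end of study page in the eCRF". Both times start at surgery. No data cut-off date is given, and no second source for the censoring date.

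**Timing (SAP 2.1).** "Main analysis will be performed after all patients had their end of treatment, data entry for all visits except the follow-up visits is complete". Its scope is broad: "Main analysis will summarize all data recorded up to the time of the database snapshot". The addendum follows study completion and is confined to follow-up data. Its list has overall survival, end-of-study details and subsequent therapy, plus an SAE listing. DFS is not on it.

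**Follow-up (Protocol 3.4 and 5.2.6).** "All enrolled patients will be followed up until the end of the study", and an individual's follow-up stops only at death or study termination. Protocol 3.7 puts LPO at about month 40 and end of study at about month 64.

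**Missing data (SAP 2.8).** The general rule is that "missing data will not be imputed and analysis is restricted on available data". The DFS/OS exception covers incomplete dates and refers back to SAP 5.2.

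**Outputs.** SAP 5.1 and 7.1.3 list the DFS and OS Kaplan-Meier tables (14.3.3 and 14.3.4, with ITT repeats) without assigning them to either analysis. SAP 5.3 asks for estimates at, for example, 12, 24 and 36 months.

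**The concern.** A Kaplan-Meier estimate needs the follow-up time of patients who have not had the event. Here that time has one source, a page that belongs to the end of a patient's participation, while the main analysis is run about two years before participation ends for most of them.

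If these patients have no usable date and are left out, inclusion depends on having had the event or having left early. The curve then tends towards the distribution of event times among patients with events, which is far below the true DFS. For OS the gap is wider: patients alive after a recurrence also lack a censoring date.

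The addendum would repair OS. It would not repair DFS, because DFS is not listed there.

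**Working it through.** **1. The plan's own timeline.** LPO at month 40 plus 24 months of follow-up gives 40 + 24 = 64 months, as Protocol 3.7 states. The main analysis can therefore fall roughly two years before most end-of-study pages are due.

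**2. What the page holds.** Listing 16.2.1.3 (SAP 7.2.1) gives its fields: date of study end, last contact alive, reason for study end, death date and cause, and pregnancy details. Someone still in follow-up has no date of or reason for study end. Listing 16.2.3.11 shows that the follow-up pages record whether the patient is alive and whether the tumour has recurred, but SAP 5.2 does not use them for censoring.

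**3. Assumptions for the size.** N = 30 (both documents). The rest are illustrative:
- uniform accrual over 36 months;
- surgery 1.7 months after entry (the pre-surgery visit is on day 43 to 50);
- snapshot at month 41;
- every recurrence entered by then;
- exponential DFS, with the protocol's 52% 5-year relapse rate standing in for the DFS event rate.

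**4. No withdrawals, closed form.**
- Hazard λ = −ln(0.48)/60 = 0.01223 per month. True DFS S(t) = exp(−λt): S(12) = 86.3%, S(24) = 74.6%.
- Time from surgery to snapshot runs uniformly from 41 − 1.7 − 36 = 3.3 to 41 − 1.7 = 39.3 months.
- Mean event-free share at the snapshot = [S(3.3) − S(39.3)]/(36λ) = (0.9604 − 0.6183)/0.4404 = 0.777.
- Patients with an event: 30 × (1 − 0.777) = 6.7. Patients open with no censoring date: 23.3.
- Kaplan-Meier on the event patients alone estimates P(T > t | event by snapshot) = {S(t)(39.3 − t) − [S(t) − S(39.3)]/λ}/36, divided by 0.223.
- At 12 months: (23.57 − 20.04)/36 = 0.0981, and 0.0981/0.223 = 44%.
- At 24 months: (11.41 − 10.40)/36 = 0.0279, and 0.0279/0.223 = 12.5%.

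**5. With withdrawals.** Patients who withdraw or are lost do have an end-of-study page and are validly censored. Simulation, 8,000 trials per row, exponential withdrawal:

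| Withdrawn by 24 months | Events | Censored with a page | Dropped | Events among those analysed | DFS at 12 / 24 months, open patients dropped | DFS at 12 / 24 months, open patients censored at snapshot |
|---|---|---|---|---|---|---|
| 0% | 6.7 | 0 | 23.3 | 100% | 44% / 12.5% | 86% / 75% |
| 5% | 6.6 | 1.1 | 22.3 | 86% | 49% / 17% | 86% / 74% |
| 10% | 6.4 | 2.3 | 21.4 | 74% | 53% / 21% | 86% / 74% |
| 20% | 6.0 | 4.6 | 19.5 | 57% | 60% / 29% | 86% / 75% |

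**6. Sensitivity.** With 25 resected patients instead of 30 (SAP 5.2 calculates neither time without a surgery date), the literal 24-month DFS is again 12.5% to about 30%. With the snapshot at month 40, 5-year event-free rates of 35 to 60% and withdrawal of 0 to 20%, 18 to 25 of 30 patients are dropped and the literal 24-month DFS is 11 to 36% against a true 66 to 82%.

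**The case against.** **The tables may be meant for the end of the study.** The SAP has one table list for both analyses, so no table is expressly reserved for the addendum. SAP 2.1 starts the main analysis when "data entry for all visits except the follow-up visits is complete", and Protocol 5.2.7 places the final analysis after the last patient's 24 months. At that point SAP 5.2 works as written. This stands as a possible reading. But the main analysis is also told to summarise everything recorded, and under the addendum-only reading DFS, a secondary endpoint, has no stated analysis. Both readings need a correction.

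**A reader might infer that the page certainly does not exist and that open patients will be dropped.** The documents do not support that certainty. The eCRF is not supplied. SAP 5.2 says that event-free patients are censored, and the two exclusions it states (incomplete surgery date, negative time) do not include a missing page. Dropping them is the literal result of applying SAP 2.8, but a programmer could improvise another date, and the censoring flags in Listing 16.2.3.6 might reveal the problem. What remains is that an open-label trial would leave this choice to someone who can see the data.

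**A reader might also infer that the curves would rest almost only on patients with events.** That holds only with few early exits: the event share falls to about 74% at 10% withdrawal and 57% at 20%.

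**The size is illustrative.** The 52% is an overall relapse rate after curative surgery, neither DFS nor specific to stage II/IIIA. Follow-up pages need not be complete at the snapshot, yet the calculation counts every recurrence. DFS and OS are descriptive, with no tests, and neither the feasibility criterion nor the early stopping rule uses them.

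**Conclusion.** The point holds as a gap between SAP 2.1 and 5.2. The only named censoring source is one that event-free patients probably do not have at the main analysis, and the later analysis at which they would have it does not list DFS. Either DFS and an interim OS are estimated at the snapshot without valid censoring dates for most event-free patients, or DFS is never analysed.

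If open patients are dropped, the bias is strongly downward in every scenario examined: about 7 to 11 of 30 patients contribute, and 24-month DFS is about 12 to 30% against an assumed 75%. This shows the direction and possible scale. It does not predict the trial's result.

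It would go too far to conclude that both secondary endpoints will be reported far below the truth. That depends on two inferences (page blank, patients dropped), and any OS error is temporary because the addendum repeats OS with complete pages. The point should be fixed before the snapshot, with moderate confidence. It is not critical, because no decision rule rests on these estimates.

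**What to change.** 1. In SAP 2.1, name DFS as well as OS in the addendum analysis. This is needed under either option below.
2. Then choose one:
   - **Addendum only.** State that Tables 14.3.3 and 14.3.4 and their ITT repeats are produced only in the addendum. The present SAP 5.2 source then suffices.
   - **Snapshot as well.** State a data cut-off and require follow-up pages to be entered up to it. In SAP 5.2, censor OS at the last documented alive date and DFS at the last documented recurrence-free date, from any visit or follow-up page on or before the cut-off, using the end-of-study page where one exists.

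DFS needs its own date because contact that shows only that the patient is alive does not show freedom from recurrence.

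The cost is SAP wording and a few programming lines. The second option also needs timely entry of follow-up pages that are collected anyway.
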